7.1.4.1 Adverse Events of Special Interest

Adverse events of special interest (AESIs) are predefined adverse events that will be specifically highlighted to the investigator and will be summarized separately. Only AESI meeting the definition of SAE will be categorized and reported as such in this study.

Reactive arthritis (ReA) or Neutropenia will be collected and analyzed as an AESI for this study.

Reactive arthritis is defined as non-purulent joint inflammation that develops in response to an infection in another part of the body. Since the inflammation is triggered by a previous condition, it is termed “reactive”. Intestinal pathogens that have been associated with reactive arthritis include *Campylobacter*, *Salmonella*, *Yersinia*, *Clostridium difficile*, and *Shigella*. If reactive arthritis is caused by an auto immune response, there is at least a possibility that it could be initiated by vaccination of susceptible people with the 1790GAHB vaccine.

For diagnosis of ReA, imaging and aspiration are not required (unless clinically indicated).

Neutropenia is defined as decrease of neutrophil count asymptotically or symptomatically with ANC $<1.8 \times 10^9/L$, occurring at 7 days after vaccination. Its graded from grade 1 to 4 basing on neutrophil counts as follows: Grade 1 ANC $1.5- <1.8 \times 10^9/L$, Grade 2 ANC $<1.5 \times 10^9/L$, Grade 3 ANC $1.0- 0.5 \times 10^9/L$, and Grade 4 $<0.5 \times 10^9/L$.

This is completely diagnosed by laboratory testing for complete blood count.

7.1.5 Methods for Recording Adverse Events and Serious Adverse Events

Findings regarding Adverse Events must be reported on an Adverse Events CRF, as specified in [section 7.1.1, Solicited Adverse Events](#), and on the VSAE form, if applicable, which is part of the Investigator Site File. All findings in subjects experiencing AEs must be reported also in the subject's source document.

All SAEs which occur during the course of the study, whether considered to be associated with the study vaccination or not and even if the information is incomplete, must be reported **within 24 hours of the site becoming aware of the event** to the Sponsor. Specific instructions and contact details for collecting and reporting SAEs will be provided to the investigator. Specifically, once an investigator becomes aware that a SAE has occurred in a study subject, the investigator (or designate) must complete a paper expedited Adverse Events report and forward it to the Sponsor **WITHIN 24 HOURS**. The report will always aimed to be completed as thoroughly as possible with all available details of the event and then dated and signed by the investigator (or designate). Even if the investigator does not have all information regarding a SAE, the report should still be completed and forwarded to the Sponsor within 24 hours. Once additional relevant information is received, the report should be updated and forwarded the Sponsor **WITHIN 24 HOURS**. The investigator will always provide an assessment of causality at the time of the initial report.

All SAEs are also to be documented on the Adverse Events CRF. Any medication or other therapeutic measures used to treat the AE will be recorded on the appropriate CRF(s) in addition to the outcome of the AE.

Only AESI meeting the definition of SAE will be categorized and reported as serious in this study by the investigator within 24 hours. However all other AESI irrespective of their grading will be recorded in the adverse event page of eCRF and the source documents.

After receipt of the initial report, representatives of the Sponsor or its designee will contact the investigator if it is necessary to obtain further information for assessment of the event. Of note, after the initial AE/SAE report, the investigator is required to proactively follow each subject and provide additional relevant information on the subject's condition to the Sponsor (within 24 hours for SAEs and Potential ImmuneMediated Disease pIMD, and within 2 weeks for pregnancies).

All SAEs must be reported by the investigator to his/her corresponding EC/IRB and/or applicable regulatory authorities in accordance with institutional policy/regulatory requirements and adequate documentation of this notification must be provided to the Sponsor.

GSK or its designee must also comply with the applicable regulatory requirement(s) related to the reporting of suspected unexpected serious adverse vaccine reactions (also known as SUSARs) to the regulatory authority(ies) and the IRB/EC. If a SUSAR or other safety signal relating to use of one of the study vaccines is reported to GSK or its designee, the Sponsor will communicate the information to the investigator and the investigator will be responsible for submitting this information to the EC/IRB and other relevant authorities.

7.1.5.1 Post-Study Events

Any SAE that occurs outside of the protocol-specified follow-up period and considered to be caused by the study vaccine must be reported to the Sponsor. These SAEs will be processed by the Sponsor as during the course of the study, until 3 months after last subject last visit. Instructions and contact details for collecting and reporting these suspected SAEs will be provided to the investigator.

7.1.6 Pregnancies

To ensure subjects' safety, each pregnancy in a subject after study vaccination must be reported to the Sponsor in due time of the site learning of its occurrence. If the subject agrees to submit this information, the pregnancy must be followed to determine outcome, including spontaneous or voluntary termination, details of the birth, and the presence or absence of any birth defects, congenital abnormalities, or maternal and/or newborn complications. This follow-up should occur even if intended duration of safety follow-up for the study has ended.

Pregnancy data must be recorded on a Pregnancy Report CRF (initial report) and Pregnancy Follow-Up CRF (outcome report) and reported to the Sponsor. Instructions and contact details for submitting the Pregnancy CRFs will be provided to the investigator.

Any pregnancy outcome meeting the definition of a SAE (see [section 7.1.4, Serious Adverse Events](#)) must also be reported on the VSAE Report Form. The following should always be considered as SAE.

- Spontaneous pregnancy loss, including:
 - spontaneous abortion, (spontaneous pregnancy loss before/at 22 weeks of gestation)
 - ectopic and molar pregnancy
 - Stillbirth (intrauterine death of foetus after 22 weeks of gestation).

Note: the 22 weeks cut-off in gestational age is based on WHO-ICD 10 noted in the EMA Guideline on pregnancy exposure (EMA, 2006). It is recognized that national regulations might be different.

- Any early neonatal death (i.e. death of a live born infant occurring within the first 7 days of life).
- Any congenital anomaly or birth defect (as per [\[CDC MACDP\] guidelines](#)) identified in the offspring of a study subject (either during pregnancy, at birth or later) regardless of whether the foetus is delivered dead or alive. This includes anomalies identified by prenatal ultrasound, amniocentesis or examination of the products of conception after elective or spontaneous abortion.

7.1.7 Safety Laboratory Measurements

For list of safety laboratory measurement, refer to synopsis [Table 2, Hematological Safety](#) [Table 3](#).

Safety laboratory measurement will be performed as described in [Section 3.5, Collection of Clinical Specimens](#).

Significant alterations in hematology will be clinically assessed by the investigator's medical judgment based on interpretation of deviations from institution's normal values.

Any abnormality in laboratory measurements classified as clinically significant must be reported in the Adverse Event CRF form.

If a subject is to have blood drawn testing for safety laboratory for repeat safety assessment (i.e., in case of markedly abnormal safety laboratory parameter), investigator's medical judgment will be applied concerning values that would trigger reanalysis and frequency of repeats. If neutropenia is observed at a visit, a complete blood count will be repeated on a weekly basis until resolution.

Safety laboratory assessments will be performed at the site laboratory, and results of these tests will be recorded in the source documents and in the CRF.

7.2 Efficacy Assessment

This study has no efficacy endpoints.

7.3 Immunogenicity Assessment

The ELISA methodology used in this study has been adopted based on scientific consensus and has been deemed appropriate to describe the immune response against *Shigella sonnei* GMMA in this study.

The measure of immunogenicity used in this study is IgG ELISA against *Shigella sonnei* OAg. The serologic assays on clinical samples will be performed at GSK, Clinical Serology Laboratory, Marburg, Germany, or a delegated laboratory. [Section 3: Study Design](#).

For reference of visits the measurements are taken, refer to [section 3.5](#) and to the Clinical Specimen Laboratory Manual.

8. STATISTICAL CONSIDERATIONS

8.1 Endpoints

8.1.1 Primary Endpoint(s)

8.1.1.1 Primary Safety Endpoint(s)

This study has no primary safety endpoint.

8.1.1.2 Primary Efficacy Endpoint(s)

This study has no efficacy measurements.

8.1.1.3 Primary Immunogenicity Endpoint(s)

The primary immunogenicity endpoint which is memory response, against the OAg of *S. sonnei* will be evaluated by measuring IgG Geometric mean concentrations (GMCs) after vaccination as determined by ELISA with O-antigen containing LPS as coating antigen.

8.1.2 Secondary Endpoint(s)

8.1.2.1 Secondary Safety Endpoint(s)

The measures of safety will include:

- a. Numbers of subjects with deviations from normal values of hematological tests after vaccination.
- b. Numbers of subjects with solicited local and systemic reactions during 7 days following vaccination. Solicited local reactions include injection site erythema, injection site induration and injection site pain; solicited systemic reactions include headache, arthralgia, chills, fatigue, malaise, myalgia, and fever (as measured orally).
- c. Numbers of subjects with reported unsolicited adverse events (of any nature and severity) during 84 days following vaccination.
- d. Number of subjects with reported SAEs throughout the study duration.

8.1.2.2 Secondary Efficacy Endpoint(s)

The study has no secondary efficacy endpoint.

8.1.2.3 Secondary Immunogenicity Endpoint(s)

- a. IgG Geometric mean concentrations (GMCs) at 7, 14, 28 and 84 days after vaccination as determined by ELISA and applicable geometric mean ratios between post vaccination and baseline samples.

b. Number and percentage of subjects with seroresponse for anti- LPS *S. sonnei* at 7, 14, 28 and 84 days after vaccination. Seroresponse is aimed to define a significant increase in post vaccination samples based on the biological performance of this specific serology assay and it is defined as follows:

- If the baseline value is greater than 50 ELISA Units (EU) then an increase of at least 50% in the post-vaccination sample as compared to baseline [i.e. $((\text{Post-vac minus baseline})/\text{baseline})100\% \geq 50\%$].
- If the baseline value is less or equal to 50 EU then an increase of at least 25 EU in the post-vaccination sample as compared to baseline [i.e. $((\text{Postvac minus baseline}) \geq 25 \text{ EU})$. Number and percentage of subjects with titers post vaccination concentration $\geq 121 \text{ EU/ml}$ for anti-LPS *S. sonnei* at 7, 14, 28 and 84 days after vaccination.

c. Number and percentage of subjects with titers post vaccination concentration $\geq 121 \text{ EU/ml}$ for anti-LPS *S. sonnei* at 7, 14, 28 and 84 days after vaccination.

A post-vaccination concentration ≥ 121 anti-LPS serum IgG units in the GVGH ELISA with O-antigen containing LPS as coating antigen corresponds to a titer of 1:800 in the ELISA method used by Cohen et al. (1989 *J. Clin. Microbiol.* 27:162). This antibody level is the median antibody concentration of a set of 87 convalescent subjects previously infected by *S. sonnei*. The value of 121 anti-LPS serum IgG units in the GVGH ELISA was determined by calibration against the Cohen ELISA (i.e., the GVGH standard serum was tested in Cohen's lab using the Cohen's methodology).

The serologic assays on clinical samples will be performed at GSK, Clinical Laboratory Science (CLS), Marburg, Germany, or a delegated laboratory.

8.1.3 Exploratory Endpoint(s)

8.1.3.1 Exploratory Safety Endpoint(s)

The study has no exploratory safety endpoint(s).

8.1.3.2 Exploratory Efficacy Endpoint(s)

The study has no exploratory efficacy endpoint(s).

8.1.3.3 Exploratory Immunogenicity Endpoint(s)

Other assays, including serum secretory IgA, might be done to further characterize the immune response to the study vaccine. The analysis will be described in the statistical analysis plan.

8.2 Success Criteria

The study has no predefined success criteria. **8.2.1**

Success Criteria for Primary Objective(s) Not applicable.

8.2.1.1 Success Criteria for Primary Safety Objective(s)

Not applicable.

8.2.1.2 Success Criteria for Primary Efficacy Objective(s)

Not applicable.

8.2.1.3 Success Criteria for Primary Immunogenicity Objective(s)

Not applicable.

8.2.2 Success Criteria for Secondary Objective(s)

Not applicable.

8.2.2.1 Success Criteria for Secondary Safety Objective(s)

Not applicable.

8.2.2.2 Success Criteria for Secondary Efficacy Objective(s)

Not applicable.

8.2.2.3 Success Criteria for Secondary Immunogenicity Objective(s)

Not applicable.

8.3 Analysis Sets

8.3.1 All Enrolled Set

All screened subjects who provide informed consent and provide demographic and/or baseline screening assessments, regardless of the subject's randomization and treatment status in the study and received a Subject ID.

8.3.2 All Exposed Set

All subjects in the enrolled set who receive a study vaccination.

8.3.3 Safety Set

Solicited Safety Set (solicited local and systemic adverse events and other solicited adverse events)

All subjects in the Exposed Set with any solicited adverse event data and/or indicators of solicited adverse events.

Unsolicited Safety Set (unsolicited adverse events)

All subjects in the Exposed Set with unsolicited adverse event data.

Overall Safety Set

All subjects who are in the Solicited Safety Set and/or Unsolicited Safety Set.

8.3.4 Full Analysis Set (FAS) Efficacy/Immunogenicity Set

Full Analysis Set Efficacy

Not applicable.

Full Analysis Set Immunogenicity

All subjects in the Enrolled Population who:

- Receive a study vaccination AND provide at least one immunogenicity data at relevant time points.

The FAS will be the primary analysis set for the immunogenicity objective.

In case of vaccination error, subjects in the FAS sets will be analyzed “as randomized” (i.e., according to the study group a subject was assigned).

8.3.5 Per Protocol (PP) Immunogenicity Set

All subjects in the FAS / Immunogenicity who:

- Correctly receive the vaccine.
- Have no protocol deviations leading to exclusion (see [section 8.3.8, Protocol Deviations](#)) as defined prior to analysis.
- Are not excluded due to other reasons defined prior to analysis (see [section 8.3.8, Protocol Deviations](#)).

PPS are subsets of FAS and should be always defined even if the objectives do not require it.

Examples for subjects excluded due to other reasons than protocol deviations are

- Subjects who withdrew informed consent.

8.3.6 Other Analysis Sets

None.

8.3.7 Subgroups Not

applicable.

8.3.8 Protocol Deviations

A protocol deviation is any change, divergence, or departure from the study design or procedures of a study protocol. A protocol deviation may be a reason to remove data from an analysis set at the time of analysis. CSR-reportable protocol deviations will be defined as exclusionary from the analysis according to protocol objectives and endpoints, which will be specified in the statistical analysis plan. In some cases exclusion of data may be due to a reason other than a protocol deviation, i.e. early termination.

8.4 Statistical Analysis Plan

8.4.1 Analysis of Demographic and Baseline Characteristics

Descriptive statistics (mean, standard deviation, median, minimum and maximum) for age and BMI at enrolment will be calculated overall and by vaccine group.

Distributions of subjects by sex and ethnic origin will be summarized overall and by vaccine group.

8.4.2 Analysis of Primary Objective(s)

8.4.2.1 Analysis of Primary Safety Objective(s)

The study has no primary safety objective.

8.4.2.1.1 Analysis of Extent of Exposure

The frequencies and percentages of subjects with vaccination will be summarized overall and by study group. Data will be tabulated for the All Enrolled Set.

8.4.2.1.2 Analysis of Solicited Local, Systemic and Other Adverse Events

All solicited adverse events will be summarized according to defined severity grading scales.

Frequencies and percentages of subjects experiencing each adverse event will be presented for each symptom severity. Summary tables showing the occurrence of any local or systemic adverse event overall and at each time point will also be presented.

Post-vaccination solicited adverse events reported from day 1 to day 7 will be summarized for the intervals day 1-3, day 4-7, day 1-7 by maximal severity and by vaccine group, excluding the 30 minute and 4 hour measurement, which will be summarized separately. The severity of solicited local adverse events, including injectionsite erythema and induration will be summarized according to categories based on linear measurement: 25 to 50 mm, 51 to 100 mm, >100mm.

Injection site pain/tenderness and systemic adverse events (except fever) occurring up to 7 days after vaccination will be summarized according to “mild”, “moderate” or “severe”.

Each solicited local and systemic adverse event will also be further summarized as “none” versus “any”.

Implausible measurements (for further definition see statistical analysis plan) will be left out of the analysis.

Use of antipyretics and analgesics will be summarized by frequency, by type of use (prophylactic versus treatment) and percentage of subjects reporting use. The influence of antipyretics and analgesics use on the occurrence of specific adverse events (e.g., fever, pain) will be assessed.

Body temperature will be summarized by 0.5 °C and 1.0 °C increments from 36.0 °C up to ≥ 40 °C.

8.4.2.1.3 Analysis of Unsolicited Adverse Events

This analysis applies to all adverse events occurring during the study, judged either as probably related, possibly related, or not related to vaccination by the investigator, recorded in AE CRF, with a start date on or after the date of vaccination. AE starting prior to the vaccination will only be listed. The original verbatim terms used by investigators to identify adverse events in the CRFs will be mapped to preferred terms using the MedDRA dictionary. The adverse events will then be grouped by MedDRA preferred terms into frequency tables according to system organ class.

All reported adverse events, as well as adverse events judged by the investigator as at least possibly related to study vaccine, will be summarized according to system organ class and preferred term within system organ class. These summaries will be presented by vaccination group and by interval of study observation. When an adverse event occurs more than once for a subject, the maximal severity and strongest relationship to the vaccine group will be counted.

Separate summaries will be produced for the following categories:

- Serious adverse events
- Adverse events that are possibly or probably related to vaccine

- Adverse events of special interest
- New onset of chronic disease
- Potential immune-mediated diseases (pIMDs) adverse event leading to withdrawal • Adverse events leading to a medically attended visit
- Adverse event by data source.

Data listings of all adverse events will be provided by subject. In addition, adverse events in the categories above will be provided as listed data.

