5.1.2 Screening

Subject identification numbers will be assigned sequentially to the subjects who have consented to participate in the study. The eligibility of the subject will be determined based on the inclusion and exclusion criteria listed in [section 4, Selection of Study Population](#) and evaluated during this screening procedure.

Prior to study enrolment, demographic data will be collected from the subject, including: age, gender, race and body mass index.

Medical history will also be collected, including but not limited to any medical history that may be relevant to subject eligibility for study participation such as prior vaccinations, concomitant medications, and previous and ongoing illnesses or injuries. Subject who participated in the H03_01TP parent trial will have their medical history since the last visit reviewed. Relevant medical history can also include any medical history that contributes to the understanding of an adverse event that occurs during study participation, if it represents an exacerbation of an underlying disease/pre-existing problem.

Review of systems is a structured interview that queries the subject as to any complaints the subject has experienced across each organ system. This will be performed before enrolment and used to guide physical examination.

Important prior and concomitant medications or vaccinations taken prior to start of study should be collected (refer to [section 6.5, Prior and Concomitant Medications and Vaccines](#) for further details).

Vital signs: heart rate, respiratory rate, diastolic and systolic blood pressure, temperature and also anthropometric measurements: height and weight will be collected

A general physical examination is to be performed by a qualified health care practitioner. “Qualified health care practitioner” refers to any licensed health care professional who is permitted by institutional policy to perform physical examinations and who is identified within the Study Staff Signature Log.

These data will be written in the source document (see [section 9.1, Source Documentation](#)).

Approximately 15 mL of blood will be obtained as part of the initial screening for hematology and serology testing (HIV, hepatitis B and C) and 25 mL for the same tests and HLA-B27 for naïve subjects. Another 20 mL of blood will be collected before vaccination on day 1 for baseline immunological testing (Refer to [section 3.5, Collection of Clinical Specimens](#)).

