7. ASSESSMENTS

7.1 Safety Assessment

The measures of safety used in this study are based on previous study data. They include a close vigilance for, and stringent reporting of selected local and systemic adverse events routinely monitored in vaccine studies as indicators of reactogenicity.

An adverse event (AE) is defined as any untoward medical occurrence in a subject or clinical investigation subject administered a pharmaceutical product at any dose that does not necessarily have to have a causal relationship with this treatment. Therefore, an AE can be any unfavorable and unintended sign (including an abnormal laboratory finding, for example), symptom, or disease temporally associated with the use of an investigational product, whether or not considered related to the investigational product. This definition includes intercurrent illnesses or injuries and exacerbation of pre-existing conditions.

For the purpose of this trial, AEs will be from the time the subject signs informed consent until Visit 4. AEs occurring after the informed consent form is signed but prior to receiving study vaccine will be documented as an adverse event and recorded within source document. However, any AEs occurring prior to receipt of any study vaccine will be analyzed separately from “treatment emergent” AEs (AEs occurring after administration of the first study vaccine). All adverse events that are serious, clinically significant as judged by the investigators, medically attended and AESI will be collected until study termination at visit 5.

Adverse events are collected as either solicited or unsolicited adverse events. Solicited events are derived from organized data collection systems, such as Subject Diaries or interview.

7.1.1 **Solicited Adverse Events**

The term “reactogenicity” refers to solicited signs and symptoms (“solicited adverse events”) occurring in the hours and days following a vaccination, to be collected by the subject for 7 consecutive days, using a pre-defined Subject Diary.

The following solicited adverse events are included in the Subject Diary. Each adverse event is to be assessed using the scoring system reported in parentheses below:

Solicited Local Adverse Events

These include erythema, induration and pain at injection site. They will be assessed using the scoring system reported in a table below. **Table 6 Grading of solicited local adverse events**

Solicited local adverse events	Grade 0 Absent	Present - Grading of Severity		

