6.5.2.3. Unsolicited Adverse Events

All the unsolicited adverse events occurring during the study, judged either as probably related, possibly related, or not related to vaccination by the investigator, will be recorded. The original verbatim terms used by investigators to identify adverse events in the CRFs will be mapped to preferred terms using the MedDRA dictionary. The unsolicited adverse events will then be grouped by MedDRA preferred terms into frequency tables according to system organ class. Adverse events judged by the investigator as at least possibly related to study vaccine will be summarized by vaccine group, according to system organ class and preferred term within system organ class. When an unsolicited adverse event occurs more than once for a subject, the maximal severity and strongest relationship to the vaccine group will be counted.

Only vaccine-emergent adverse events (see **section 7.1** of protocol for definition) will be analyzed, i.e., excluding those after a subject has given informed consent but before vaccination.

The summaries will be presented for all study period and will include frequency distributions of the different adverse events:

- Onset between day 1 and study termination (all study period).

The analysis of unsolicited adverse events comprises the following categories:

- Any unsolicited adverse event.
- Possibly or probably related unsolicited adverse events.
- Unsolicited adverse events leading to death.
- Serious adverse events.
- Possibly or probably related serious adverse event.
- Unsolicited adverse events leading to premature withdrawal from study.
- Unsolicited adverse events leading to hospitalization.
- Unsolicited adverse events of special interest.

- Solicited adverse events continuing beyond day 7 will be coded by MedDRA and combined with the respective unsolicited adverse events.

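### The unsolicited AE tables are selected by onset with no rule for worsening after the injection, and the Day 1 boundary is defined in two incompatible ways

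*Protocol*

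**What the plan says.** Protocol 8.4.2.1.3 (same text in Versions 1 and 2) applies the unsolicited AE analysis to events in the AE CRF "with a start date on or after the date of vaccination. AE starting prior to the vaccination will only be listed". Its separate summaries (serious, special interest, medically attended and others) fall under the same rule.

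Protocol 7.1 collects AEs from consent, and screening can be up to 21 days before vaccination. It defines treatment-emergent events as "AEs occurring after administration of the first study vaccine". It says that "any AEs occurring prior to receipt of any study vaccine will be analyzed separately from" these, and that an event between consent and vaccination "will be documented as an adverse event and recorded within source document". On what counts as an AE, it adds: "This definition includes intercurrent illnesses or injuries and exacerbation of pre-existing conditions".

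SAP 6.5.2.3 analyses only vaccine-emergent events, referring to protocol 7.1 for the definition and "excluding those after a subject has given informed consent but before vaccination". The interval for its summaries is "Onset between day 1 and study termination (all study period"). SAP section 9 declares no change from the planned analyses.

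**The concern.** A definition of treatment-emergent events usually has two limbs: new onset after treatment, and worsening after treatment of something already present. Only the first is written here. A complaint that starts in screening and becomes severe, serious or medically attended after the injection is of direct interest for vaccine safety, yet a table selected on onset does not show it. The omission works in one direction, towards undercounting.

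The Day 1 boundary raises a separate problem. Study procedures take place that day before the injection; protocol 5.1.2 says "Another 20 mL of blood will be collected before vaccination on day 1 for baseline immunological testing". A faint or bruise from that draw has a start date equal to the vaccination date but precedes the vaccine.

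Safety is a secondary objective, and SAP 6.5.2 shows primed subjects beside placebo-plus-naïve subjects. With groups this small, a single classification changes a displayed percentage visibly.

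**Working it through.** No figure in the plan depends on this rule, so the check applies each written rule to two cases.

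**Case A: unsolicited event, onset between consent and injection, worse after the injection.**

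1. Kept on one record, the event has a start date before vaccination. Protocol 8.4.2.1.3 then lists it only, and SAP 6.5.2.3 excludes it.
2. If the site enters the worsening as a new event with its own later start date, it is tabulated. The AE definition in 7.1 permits this; no section of either document requires it.
3. Inclusion therefore depends on recording practice that the documents do not fix.
4. The serious and medically attended summaries in protocol 8.4.2.1.3, and the serious, hospitalization and withdrawal categories in SAP 6.5.2.3, are drawn from the same selected events and inherit the gap. The special-interest summary does too, although there the case is hard to reach: exclusion criteria 24 and 25 remove a low neutrophil count at screening and a history of reactive arthritis.

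**Case B: event on Day 1, before the injection.**

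| Text | Result |
|---|---|
| Protocol 8.4.2.1.3, start-date phrase | Counted (start date equals vaccination date) |
| Protocol 8.4.2.1.3, next sentence | Listed only |
| Protocol 7.1, treatment-emergent definition | Not counted |
| SAP 6.5.2.3, vaccine-emergent sentence | Not counted |
| SAP 6.5.2.3, summary interval | Counted (interval opens at Day 1) |

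Two texts admit the event and three reject it. Protocol 6.6 requires the time of vaccine administration to be logged, but neither document mentions a time of AE onset, so a programmer could not apply the stricter reading from dates alone.

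**Scale.** Group sizes come from protocol Table 1 and SAP Table 2-1.

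- Primed: 5 + 4 + 2 + 4 + 5 = 20, so one subject is 1/20 = 5.0 percentage points.
- First dose: 4 + 26 = 30, so one subject is 1/30 = 3.3 percentage points.

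The number of subjects affected cannot be derived, because the documents give neither the rate of events ongoing at injection nor the rate of worsening.

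**The case against.** A reader might infer that a worsened screening event disappears from every AE table. The documents do not support that. The solicited tables (SAP 6.5.2.2) are built from reports after the injection by maximal severity, with no start-date filter. Solicited events enter the combined table (SAP 6.5.2.4) whatever their duration. Worsening in haematology shows in the shift tables (SAP 6.5.2.5). A headache or fatigue that began in screening and is entered in the diary is therefore tabulated.

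A reader might also infer that Day 1 events before the injection are definitely counted. Three of the five statements above reject them, so the text is contradictory and does not settle the matter.

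Nor does the instruction in 7.1 to record pre-vaccination events in source show that they never reach the database. It does not say only there, and 8.4.2.1.3 promises to list them.

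The remaining arguments are about importance. Subjects are healthy volunteers, unstable conditions are excluded, eligibility is rechecked before injection, all analyses are descriptive, and by-subject listings of all AEs would keep the event visible. Instructions on splitting records may exist in CRF guidance outside these documents. All of this stands and makes the case uncommon. It does not supply a worsening rule, and a listing does not correct a percentage in a table. Protocol 7.1.4 itself lets hospitalization for a worsened pre-existing condition count as serious; the analysis rule has no counterpart.

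**Conclusion.** The point holds for unsolicited AEs. As written, the plan can leave post-injection worsening out of the unsolicited tables and the summaries cut from them. This rests on the event being kept on one record, which neither document requires or forbids. The Day 1 wording is inconsistent and needs reconciling, with no presumption about which reading would have been programmed.

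The likely effect is small in number and cannot be quantified from the documents; each subject affected moves a group percentage by 5.0 or 3.3 points at the planned sizes. For worsening, the error is an undercount. Nothing shows that it would differ between primed and first-dose subjects. The primary immunogenicity objective is untouched.

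**What to change.** Put one definition in protocol 8.4.2.1.3 and SAP 6.5.2.3, and use it for all unsolicited tables and their sub-summaries: a vaccine-emergent AE is one with onset after the injection, or one present before it that increases in severity or becomes serious after it. Align protocol 7.1, including whether earlier events are listed or analysed separately. If only the SAP is revised, record the change in its section 9.

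Classify Day 1 onsets by onset time or by a before/after-injection flag, and word the SAP interval to match. Confirm that pre-vaccination AEs are entered in the AE CRF, with severity over time or a new record on worsening, so that the second limb can be programmed.

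The cost is a few sentences in each document and one CRF field. AE counts may come out slightly higher.
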